*: The allowed window period between visits in Treatment period and Follow-up period is ± 1 day provided that 2 consecutive visits are 3 days apart at a minimum. Every effort should be made to schedule every visit on the exact Day (which is relative to the Baseline visit or [Visit 1]) as described in above Schedule of Assessments ([Table 1](#)) without the window.

**: The Visits 2, 4, 6, and 8 are optional.

- a. To take place within 15 days prior to first administration of the Investigational Medicinal Product (IMP) at Visit 1.
- b. No study-related assessment is to be carried out before the patient has signed informed consent.
- c. A complete physical examination will be performed at Screening, Visit 7, and at Visit 16/EoS/ED. An abbreviated examination will be done at all other visits. On dosing days, physical examination including weight measurement should be performed pre-dose.
- d. Height should only be measured at Screening (and Body Mass Index [BMI] to be calculated accordingly at Screening only).
- e. Randomization to be performed only after confirmation of eligibility of the patient including the MG-ADL score assessed at Visit 1 and prior to dosing at Visit 1. The assessments for vital signs, urinalysis, and anti-drug antibodies, must be performed pre-dose at visits when the Investigational Medicinal Product (IMP) is administered (Visits 1, 3, 5, and 7). **Efficacy assessments** scheduled on designated Days should be completed pre-dose on each dosing day and **should be performed prior to any other study specific assessment**, except for obtaining informed consent at Screening. **Efficacy assessments** should be performed in the following sequence (at each study visit including these assessments): **MGQoL15r, MG ADL, QMG, and MGC**. Cholinesterase inhibitors must be held for at least 12 hours before the MGQoL15r, MG-ADL, QMG, and MGC assessments (consistent with the revised manual for the QMG test as recommended by the Myasthenia Gravis Foundation of America Inc [MGFA])¹. A total score ≥ 5 on the MG-ADL with more than 50% of this score attributed to non-ocular items should be met at both Screening and Baseline (Visit 1) to confirm eligibility.

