- f. Sampling for clinical laboratory tests is to be performed pre-dose on dosing days and tests will include hematology (hemoglobin, platelet count, white blood cell count with differential); blood chemistry (including creatinine, creatinine clearance, blood urea nitrogen [BUN], glucose, alanine aminotransferase [ALT], aspartate aminotransferase [AST], total bilirubin, gamma-glutamyl transferase [GGT], C-reactive protein [CRP], alkaline phosphatase [AP], lactate dehydrogenase [LDH], uric acid, albumin, potassium, calcium, sodium, thyroglobulin, International normalized ratio or activated partial thromboplastin time [aPTT], CD19 counts). Patients need to be fasting for at least 8 hours prior to this sampling.
- g. Sampling for pharmacodynamic biomarkers is to be performed pre-dose on dosing days and include anti-AChR antibodies and immunoglobulin G and its sub-types. Analysis of anti-AChR antibodies will include anti-AChR binding antibodies and anti-AChR blocking antibodies. IgG measurements include total IgG, IgG subtypes (IgG 1, IgG 2, IgG 3, and IgG 4). In addition, IgA, IgD, IgE, and IgM will also be assessed.
- h. ECG (heart rate, PR, QT, and QRS interval) will be read locally and should be performed pre-dose on dosing days.
- i. Pharmacokinetic (PK) assessments should be done both pre- and post-dose (within 30 minutes prior to start of infusion for pre-dose sample and within 30 minutes after end of infusion for post-dose sample) on all IMP infusion days.
- j. Serum pregnancy test must be performed in women of childbearing potential at Screening from the blood sample collected for clinical laboratory tests at the central laboratory.
- k. Urine pregnancy test will be performed locally pre-dose at Visits 1, 3, 5, 7, 11, and 16/EoS/ED.
- l. Tests to assess HbsAg, anti-HCV antibodies, Follicle stimulating hormone (FSH), HIV antibodies and tuberculosis serology (QuantiFERON®-TB Gold) test will be performed at the central laboratory.

argenx
ARGX-113-1602, Version 2.0
ARGX-113

- m. A blood sample for the optional pharmacogenetic testing is to be collected before the first dose of the Investigational Medicinal Product is administered at Visit 1 (Baseline) after a separate pharmacogenetic ICF has been signed, and will be stored for pharmacogenetic analysis. Only if the blood sample at Visit 1 is missed, the sample should be drawn at Visit 3 before the administration of the Investigational Medicinal Product.

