Disease deterioration during Treatment period	After consultation with the Medical Monitor , discontinue patient from Study Treatment, initiate rescue therapy and follow-up for 30 days after the early discontinuation visit or until satisfactory resolution/stabilization.	After consultation with Medical Monitor and prior to start on rescue therapy, all Visit 16 assessments should be completed. Patients will be discontinued from the study and followed up for safety for an additional 30 days or until satisfactory resolution/stabilization.	Patients will be analyzed as part of Safety and Efficacy analysis and such a patient will not be replaced
Disease deterioration after Treatment period: In case of disease deterioration after Treatment period , the safety and efficacy assessments per Follow-up period of Table 1 (Visit 16) must be completed along with a follow-up for 30 days after the early discontinuation visit or until satisfactory resolution/stabilization where possible and Medical Monitor should be consulted.	Not Applicable.	Patient's study continuation must be assessed by the Investigator, discussed with the Medical Monitor and/or Sponsor's Medical Director based on clinical examination. Possible examples of worsening include: 
 • Severe deterioration where it may not be possible for patient to continue in the study. • The "End of Treatment Effect" whereby the patient's condition is worsening after any initial improvement while on the study. Prior to initiating rescue therapy, all Visit 16 assessments should be completed and patient should be followed up for safety for an additional 30 days or until satisfactory resolution/ stabilization.	Patients will be analyzed as part of Safety and Efficacy analysis and such a patient will not be replaced

Scenario	Discontinuation from Study Treatment	Discontinuation from Study	Replacement if necessary

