7.9.2 Rescue Therapy

Patients are eligible for rescue therapy as judged by the Investigator on the basis of parameters such as changes in MGQoL15r, MG-ADL, QMG, and MGC on any study day. Rescue therapy will be determined by the Investigator based on an overall clinical assessment and could include IVIg, PE, increase in the dose and frequency of SoC or any other treatment chosen by the Investigator. In this study, ARGX-113 may interfere with the efficacy or duration of efficacy of IVIg considering the half-life of IVIg. Additional details about ARGX-113 is present in [Section 2.2](#).

In case a patient needs rescue therapy according to the treating Investigator, the [Medical Director](#) at the Sponsor should be informed in addition to the [Medical Monitor](#) at the Sponsor's designated contract research organization (CRO, Quintiles); where possible prior to actual implementation of the rescue therapy.

If rescue therapy is administered, patients need to be discontinued from the study. For patients who discontinue the study early, all the procedures listed for the Early Discontinuation (ED) visit (same procedures as for the End-of-Study [EoS] visit or Visit 16) in the Schedule of Assessments ([Table 1](#)) are to be performed (early discontinuation visit) prior to starting on rescue therapy wherever possible.

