14.2 Appendix 2: Quantitative Myasthenia Gravis score

QUANTITATIVE MYASTHENIA GRAVIS TESTING FORM

Patient Name: _____ Patient #: _____ Date: _____
MR#: _____ DOB: _____ Sex: _____ Ht.(in) _____ Wt.(kg): _____
Evaluator: _____ Handedness: _____ Leggedness: _____ Time of Exam: _____
Anticholinesterase Medication: _____
Comments: _____

A large black rectangular box is positioned below the patient information, likely used to redact sensitive data.

argenx
ARGX-113-1602, Version 2.0
ARGX-113
[REDACTED]

TOTAL QMG SCORE: _____

argenx
ARGX-113-1602, Version 2.0
ARGX-113

GENERAL INSTRUCTIONS

1. Patients must be off pyridostigmine (or any acetylcholinesterase inhibitor medication) for twelve (12) hours prior to testing, (if medically safe to do so).
2. Perform the tests in the order given in this Manual and shown on the Videotape.
3. Calibrate the respiratory equipment on the day of the test, per manufacturers' instruction, before the test begins. Place the calibration record in folder in an accessible place.
4. For all measurements, record actual numbers as well as grade, i.e., if it takes 30 seconds before a patient sees double, record on the far right box 30/1 for 30 seconds and a grade of 1.
5. Patients must remain seated for the respiratory test.
6. At the end of the scoring sheet, add up the grade for that patient and that becomes the Total QMG Score.

argenx
ARGX-113-1602, Version 2.0
ARGX-113

QUANTITATIVE MG SCORE

I. DOUBLE VISION:

Patients' preparation: Patient is sitting. Ask if the patient is experiencing double vision looking straight ahead. If yes, record 0/3 (actual time/grade) on the scoring sheet. If no, ask the patient to look to the right for just an instant and then to the left without moving their head. If the patient sees double in only one direction, record side and record result as 0/3. If there is no eye movement, record as 0/3. If the patient does not see double, or sees double in both directions, have them perform the test as described below gazing to the right.

Explanation to patient: "I need for you to face forward. When I ask, look over to your right (left) side without turning your head. If or when you start to see double, please let me know."

Notes to examiner: Patient's head will usually start to turn in the direction of the gaze. Try to maintain the head in a forward position. Record the time and grade. Example: double vision is evident at 15 sec. In the scoring section, record 15/1.

II. PTOSIS (upward gaze):

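### The protocol conflicts on what comes before rescue: Table 2 carries no qualifier where Sections 7.9.2 and 6.6 do, and the 12-hour drug hold omits its manual's safety condition

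*Protocol*

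**What the plan says.** **Order of steps before rescue.** In Protocol Section 5.3.4, Table 2, the row for deterioration during the Treatment period says in its study-discontinuation column: "After consultation with Medical Monitor and prior to start on rescue therapy, all Visit 16 assessments should be completed". Its treatment-discontinuation column also puts Medical Monitor consultation first, and then has the site "discontinue patient from Study Treatment, initiate rescue therapy and follow-up for 30 days after the early discontinuation visit". The row for deterioration after the Treatment period says in one column: "Prior to initiating rescue therapy, all Visit 16 assessments should be completed". The scenario column of that row contains a feasibility qualifier, but it is unclear whether this covers the assessments, the 30-day follow-up or both.

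Section 7.9.2 states that the early-discontinuation procedures, which are those of Visit 16, "are to be performed (early discontinuation visit) prior to starting on rescue therapy wherever possible". It asks that the Medical Director and Medical Monitor be informed, "where possible prior to actual implementation of the rescue therapy". The Synopsis and Section 5.1 treat the contact step in the same way. Section 6.6, which defines the early-discontinuation visit, also limits the set to what is possible. The closing paragraph of Section 5.3.4 asks for the set with no qualifier.

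**Preconditions of the assessments.** The Visit 16 set includes MGQoL15r, MG-ADL, QMG and MGC. Table 1, note e, says: "Cholinesterase inhibitors must be held for at least 12 hours before the MGQoL15r, MG-ADL, QMG, and MGC assessments". The Synopsis, Section 5.1 and the note to inclusion criterion 5 repeat the hold. For the clinical laboratory tests, Table 1, note f, says: "Patients need to be fasting for at least 8 hours prior to this sampling". The QMG manual reproduced in Appendix 14.2 words the hold differently: "Patients must be off pyridostigmine (or any acetylcholinesterase inhibitor medication) for twelve (12) hours prior to testing, (if medically safe to do so").

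**The concern.** Rescue can be needed on any study day, so the patient cannot prepare for the pre-rescue visit as for a scheduled one. A site that works from Table 2 and note e could reasonably conclude that a worsening patient should first be discussed with the Medical Monitor, then come off cholinesterase inhibitors for 12 hours and fast for 8, then complete every Visit 16 assessment, and only then receive rescue. A site that works from Section 7.9.2 would not conclude this.

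Patient safety is the main stake: the timing of rescue would depend on which section the site consulted. Consistent conduct is also at stake, because the same action could be classed differently at two sites. A lesser issue is that rescued patients leave the study under Section 7.9.2, so the pre-rescue scores are normally their last efficacy values.

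**Working it through.** The plan gives no figure on this point, so the check is a comparison of text and a bound on the wait.

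**1. The instructions side by side**

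| Step | Table 2, during treatment | Table 2, after treatment | Section 7.9.2 | Section 6.6 |
|---|---|---|---|---|
| Contact with Medical Monitor | Consultation, before rescue | Consultation, not placed before rescue | Informed, before rescue if possible | Not addressed |
| Visit 16 set before rescue | Yes, no qualifier | Yes, no qualifier in one column; qualifier of unclear scope in another | Yes, if possible | Same set, if possible; does not mention rescue |

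The safety-concern rows of Table 2 carry explicit qualifiers about what is possible and safe. A site could therefore read their absence from the during-treatment deterioration row as deliberate.

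**2. The hold**

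- The protocol body states the hold as mandatory and names no exception. The Synopsis, Section 5.1, the criterion 5 note and note e all describe it as consistent with the QMG manual.
- The manual makes the same 12 hours conditional on medical safety.
- The visit list for the hold in the Synopsis and Section 5.1 names Visit 16 but not the early-discontinuation visit. Section 6.6 gives that visit the Visit 16 content, and note e ties the hold to the assessments themselves. Whether the hold applies before rescue is therefore left to inference.

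**3. The wait implied by a literal reading**

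Let *h* be the hours since the last cholinesterase-inhibitor dose and *f* the hours since the last food, both at the decision to rescue. The hold and the fast can run together, so the wait is the larger of the two remaining times:

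wait = max( max(0, 12 − *h*), max(0, 8 − *f*) )

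- On a cholinesterase inhibitor, dose and meal just taken (*h* = 0, *f* = 0): max(12, 8) = 12 hours.
- On one, *h* ≥ 12 and *f* ≥ 8: max(0, 0) = 0 hours.
- Not on one, just eaten (*f* = 0): 8 hours. Already fasted (*f* ≥ 8): 0 hours.

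The two minimums do not add to 12 + 8 = 20 hours. The time taken by the consultation and the assessments would come on top; the documents do not give it.

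**4. One action under two sections**

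Suppose the investigator judges that the patient cannot wait and gives rescue before the assessments are complete. Under Section 7.9.2 this is compliant. Under the during-treatment row of Table 2 it departs from the stated order. Section 5.3.7 allows departures for patient safety but requires them to be reported immediately.

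**5. The data**

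SAP Section 6.4 maps early-termination data to the next available visit for by-visit summaries, and SAP Section 7.3 imputes nothing. The SAP does not separate scores taken on a cholinesterase inhibitor from scores taken off it. Inclusion criterion 3(iii) recognises improvement on these drugs, so an on-drug score set against an off-drug baseline could understate deterioration. With 12 patients planned per arm, one patient is 1/12, about 8% of an arm. The documents give neither the number rescued nor the size of any score shift.

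**The case against.** The strongest reply is that the protocol, read as a whole, does not oblige any site to withhold rescue. Table 2 says what should be done, not what must be. Section 6.6 limits the early-discontinuation set to what is possible, Section 5.3.7 permits deviation for safety, Section 6.0 puts the patient's safety and well-being first when a procedure cannot be performed, and Section 7.9.2 leaves rescue to the investigator's overall clinical assessment. This stands as far as it goes: the order in Table 2 is unqualified, but it is not an absolute bar. It does not remove the conflict, since a safety deviation still has to be reported whereas Section 7.9.2 calls for none.

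Appendix 14.2 is also part of the protocol, and Section 8.2.3 refers to it for QMG testing. The safety condition is therefore present, though not repeated where the hold is imposed. That is fair: it is a gap in cross-reference, not a deletion.

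Three stronger inferences are tempting, and the documents do not support them:

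- *Every rescued patient is delayed.* The hold matters only for a patient on a cholinesterase inhibitor whose last dose was less than 12 hours earlier, and the fast only for an unfasted patient. The after-treatment row also has its own qualifier.
- *The softer wording of Section 7.9.2 produces on-drug scores.* That wording governs whether the procedures precede rescue. It does not relax the hold. On-drug scores could arise only through the manual's safety condition or through the omission of the early-discontinuation visit from the hold's visit list.
- *The MMRM is biased.* SAP Section 6.4 states its mapping for by-visit summaries and does not expressly extend it to the model. Efficacy is secondary, exploratory and not formally powered, and the QMG form already has fields for anticholinesterase medication and time of examination, though no field for the time of the last dose is visible.

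**Conclusion.** The concern holds as an internal inconsistency with a possible consequence for patient safety. The during-treatment row of Table 2 conflicts with Sections 7.9.2 and 6.6 on the assessments, and with Section 7.9.2, the Synopsis and Section 5.1 on contact with the Medical Monitor. The after-treatment row conflicts in part. The hold in the protocol body does not carry the condition stated in Appendix 14.2, and its application to a pre-rescue visit is not stated.

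The literal wait is 0 to about 12 hours for a patient on a cholinesterase inhibitor, and up to about 8 hours for an unfasted patient not on one. These bounds assume that the hold and fast run in parallel, that both apply to the pre-rescue visit, and that the safety and feasibility provisions elsewhere are not invoked. The effect on efficacy results is possible but speculative, and the documents do not allow it to be sized.

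**What to change.** The sponsor should reconcile two sets of passages in a single statement:

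- both deterioration rows of Table 2, the closing paragraph of Section 5.3.4, Section 6.6 and Section 7.9.2, with the contact wording in the Synopsis and Section 5.1;
- the hold in the Synopsis, Table 1 note e, Section 5.1 and the criterion 5 note, with the condition in Appendix 14.2.

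The statement should say whether Medical Monitor consultation, the assessments, the hold and the fast each apply before rescue, and whether the hold covers the early-discontinuation visit. Which clinical rule to adopt is for the sponsor. The cost is a short protocol clarification communicated to the sites.

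Optional and secondary: record the time of the last cholinesterase-inhibitor dose at pre-rescue and early-discontinuation assessments, and flag scores taken within 12 hours of it in the listings. This costs one eCRF field and one flag. The SAP should also say whether mapped early-termination scores enter the MMRM.

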5.3.4 Early Discontinuation from the Study Treatment or Study

The criteria for enrollment and randomization are to be followed explicitly. If it is noted that a patient who does not meet the inclusion and exclusion criteria is inadvertently randomized and dosed, the [Medical Monitor](#) at Sponsor's designated CRO (Quintiles) and the Sponsor's [Medical Director](#) must be contacted immediately for discussion on how to proceed with the patient. The patient should be discontinued from the study if there is any compelling safety concern for the patient to continue. The various scenarios that may occur leading to discontinuation of the patient from study and/or treatment is detailed in [Table 2](#).

Table 2 Potential Scenarios for Early Discontinuation from Study and Treatment

Scenario	Discontinuation from Study Treatment	Discontinuation from Study	Replacement if necessary
Safety Concern during Treatment period: In case of a safety concern during Treatment period , Medical Monitor should be consulted and the safety and efficacy assessments per Follow-up period of Table 1 (Visit 9 to Visit 16) must be completed wherever possible.	Discontinue patient from Study Treatment.	Patient does not need to be discontinued from the study depending on the severity and nature of safety event but discontinuation from the study needs to be discussed with the Medical Monitor and/or Sponsor's Medical Director . Wherever possible and appropriate/safe, the patient should continue the schedule of assessments for the Follow-up Period of Table 1 (Visit 9 to Visit 16).	Patients will be analyzed as part of Safety and Efficacy analysis and such a patient will not be replaced.
Safety Concern after Treatment period: In case of a safety concern after Treatment period , the safety and efficacy assessments per Follow-up period of Table 1 (Visit 9 to Visit 16) must be completed where possible and Medical Monitor should be consulted.	Not Applicable.	Patient does not need to be discontinued from the study depending on the severity and nature of safety event but discontinuation from the study needs to be discussed with the Medical Monitor and/or Sponsor's Medical Director . Wherever possible and appropriate/safe, the patient should continue the schedule of assessments in the Follow-up Period of Table 1 (Visit 9 to Visit 16).	Patients will be analyzed as part of Safety and Efficacy analysis and such a patient will not be replaced.

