Voluntary Discontinuation from IMP or Major Protocol Deviation(s) possibly leading to (Details in a separate Manual) discontinuation from IMP during Treatment period: The Schedule of Assessments for dosing and safety and efficacy evaluations per Table 1 must be performed whenever possible and must be discussed with the Medical Monitor on a case-by-case basis.	In case of voluntary discontinuation during Treatment period or any major protocol deviation(s) possibly leading to discontinuation from IMP during treatment period, a patient should be discontinued from the study treatment.	Patient does not need to be discontinued from the study but discontinuation from the study needs to be discussed with the Medical Monitor and/or Sponsor's Medical Director . And wherever appropriate, patient should continue the schedule of assessments.	Patient will not be replaced if he/she receives at least 3 infusions and completes the Follow-up assessments as indicated in Table 1 with at least 2 weeks of Follow-up post last dose. Patient may be replaced if he/she receives less than 3 infusions and/or cannot complete at least 2 weeks of Follow-up post last dose as indicated in Table 1 .
Major Protocol Deviation(s) (Details in a separate Manual) after Treatment period: The safety and efficacy assessments per Follow-up period of Table 1 (Visit 8 to Visit 16) must be completed where possible and Medical Monitor should be consulted.	Not Applicable.	Patient does not need to be discontinued from the study but discontinuation from the study needs to be discussed with the Medical Monitor and/or Sponsor's Medical Director . Wherever appropriate, patient should continue the schedule of assessments.	Such patients may only be replaced they cannot complete at least 2 weeks of Follow-up post last dose as indicated in Table 1 .

During the study, in case of situations that occur apart from the scenarios described above, the decision to replace patients must be made on a case-by-case basis in consultation with the [Medical Monitor](#) at the Sponsor's designated contract research organization (CRO, Quintiles) and/or the [Medical Director](#) at the Sponsor's end.

In addition, patients must be discontinued early from the study in the following circumstances:

- Pregnancy.
- Lack of efficacy as judged by the Investigator.
- Emergency unblinding.
- Physician decision.
- Lost to follow up.
- On request of the Sponsor.

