7.9.1 Prohibited Medications during the Study

The following medications will not be permitted during the study and will result in early discontinuation from the study when they need to be started:

- Any IgG therapy;
- Introduction of a new immunosuppressant that the patient was not already taking at Screening;
- Dose increase in the immunosuppressant that the patient was taking from Screening;

- Rituximab, belimumab, eculizumab, or any monoclonal antibody for immunomodulation;
- Vaccines;
- Therapeutic PE.

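### Investigator-judged lack of efficacy forces exit from the whole study, so later observed efficacy summaries may describe a selected sample; stopping IMP at most, with assessments continued, would be a cheap improvement

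*Protocol*

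**What the plan says.** Protocol 5.3.4 closes with a list headed "In addition, patients must be discontinued early from the study in the following circumstances". The list includes "Lack of efficacy as judged by the Investigator", alongside pregnancy, emergency unblinding, physician decision, loss to follow-up and Sponsor request. No score, time point or consultation is attached to the lack-of-efficacy item.

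Table 2 in the same section is more retentive for other events. For a safety concern during treatment: "Wherever possible and appropriate/safe, the patient should continue the schedule of assessments for the Follow-up Period". For a voluntary IMP stop or a major deviation during treatment, the patient need not leave, and "wherever appropriate, patient should continue the schedule of assessments".

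Lack of efficacy is not the only outcome-related exit. For deterioration during treatment, Table 2 says: "Patients will be discontinued from the study and followed up for safety for an additional 30 days". Section 7.9.2 says: "If rescue therapy is administered, patients need to be discontinued from the study". Starting a medication prohibited under 7.9.1 "will result in early discontinuation from the study when they need to be started".

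A patient who leaves has one early discontinuation visit with the Visit 16 procedures. SAP 6.4 maps it to the next visit number. SAP 7.3 imputes nothing and relies on MMRM for missing efficacy data. SAP 15 also summarises observed scores by visit, shows box plots, and analyses maximum reduction by ANCOVA. SAP 6 routinely leaves missing values out of percentage denominators.

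**The concern.** The rule ends data collection because of a judgement on the outcome itself, although that judgement need not involve any change of treatment. It is blinded and applies to both arms. If the drug works, however, more placebo patients would be expected to meet it.

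The secondary endpoints run to Visit 16. If poorer placebo patients stop contributing, the remaining placebo patients look better than the arm as a whole, and the displayed by-visit difference narrows. Maximum reduction moves the other way: a leaver stays in the FAS but has fewer visits in which to reach a best score, so the placebo maximum is understated. Later ADA and IgG samples are lost as well, and adverse-event follow-up is shorter for early exits. Appendix 14.6 says the descriptive efficacy results are meant to help design later studies, so these displays are what readers will use.

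**Working it through.** **Source of the SDs.** Appendix 14.6 gives SD 1.80 (active) and 3.72 (placebo), difference 4.0, two-sided alpha 0.05 and 10 per group for 80% power. With unequal variances, SE = sqrt(1.80²/10 + 3.72²/10) = 1.307, 4.0/1.307 = 3.06 and Satterthwaite df = 13.0, giving power 80.8%. The plan's figure reproduces. These SDs are for scores; using them for change is an assumption.

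**Assumptions of the illustration (not in the documents).** Change is normal, with negative values meaning improvement. The decision is taken at Visit 9. Mean placebo change mu is -1 or -2, SD is 1.8 or 3.72, and the correlation rho between visits is 0.5 or 0.7. Patients worsening by c points or more leave through deterioration or rescue anyway and are not charged to this item. The item removes patients with change from 0 to below c, with c = 2 (the size of the SAP 18 MG-ADL improvement threshold) or c = 1.

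**Formulas.** If only patients with Visit 9 change below t remain, the later observed mean shifts by B(t) = -rho × SD × phi(z)/Phi(z), with z = (t - mu)/SD. The part due to this item is B(0) - B(c). The exit share is Phi((c - mu)/SD) - Phi(-mu/SD). Net bias in the difference is the placebo bias minus the active bias.

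**Worked case:** mu = -1, SD = 3.72, rho = 0.7, c = 2.
- Placebo: B(0) = -0.7 × 3.72 × 0.3848/0.6060 = -1.654; B(2) = -0.7 × 3.72 × 0.2882/0.7900 = -0.950; item bias = -0.704.
- Active, 2 points better (mu = -3): B(0) = -0.950; B(2) = -0.7 × 3.72 × 0.1617/0.9105 = -0.462; item bias = -0.488.
- Net: 0.704 - 0.488 = 0.216 points toward zero.

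**All cases, 2-point effect and the same SD in both arms** (bias as points too favourable; net as narrowing of the difference):

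| mu | SD | rho | c = 2: exits placebo / active | placebo bias | net | c = 1: exits placebo / active | placebo bias | net |
|---|---|---|---|---|---|---|---|---|
| -1 | 1.8 | 0.5 | 24.1% / 4.5% | 0.339 | 0.252 | 15.6% / 3.5% | 0.209 | 0.146 |
| -1 | 1.8 | 0.7 | 24.1% / 4.5% | 0.474 | 0.353 | 15.6% / 3.5% | 0.293 | 0.205 |
| -1 | 3.72 | 0.5 | 18.4% / 12.1% | 0.503 | 0.154 | 9.9% / 6.9% | 0.270 | 0.076 |
| -1 | 3.72 | 0.7 | 18.4% / 12.1% | 0.704 | 0.216 | 9.9% / 6.9% | 0.378 | 0.106 |
| -2 | 1.8 | 0.5 | 12.0% / 1.3% | 0.193 | 0.163 | 8.5% / 1.0% | 0.129 | 0.106 |
| -2 | 1.8 | 0.7 | 12.0% / 1.3% | 0.270 | 0.229 | 8.5% / 1.0% | 0.181 | 0.149 |
| -2 | 3.72 | 0.5 | 15.4% / 8.8% | 0.427 | 0.156 | 8.5% / 5.2% | 0.233 | 0.078 |
| -2 | 3.72 | 0.7 | 15.4% / 8.8% | 0.597 | 0.218 | 8.5% / 5.2% | 0.326 | 0.110 |

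Of 12 placebo patients, that is 1.4 to 2.9 exits (c = 2) or 1.0 to 1.9 (c = 1). If the active arm is 4 points better with SD 1.8, fewer than 0.3% of active patients leave, so the net bias is close to the placebo figure. If only half of the 0-to-c group is judged a failure, the placebo bias is 0.09 to 0.31 (c = 2) or 0.06 to 0.18 (c = 1).

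**Other outputs, by simulation under compound symmetry.** Placebo maximum reduction is understated by 0.07 to 0.26 (c = 2) or 0.05 to 0.14 (c = 1). For an MMRM-type estimate with known covariance and 12 per arm, absolute Visit 16 bias is at most 0.013. Its SE rises 2% to 9% (c = 2) or 1% to 5% (c = 1), which is optimistic because a real MMRM must estimate the covariance.

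**Data lost per Visit 9 exit.** Five of 9 post-baseline efficacy visits and 5 ADA visits (10, 11, 12, 14, 16), and 7 IgG visits (10 to 16), partly offset by one early discontinuation visit. Adverse events are followed for 30 days after that visit: Day 29 + 30 = 59 against Day 78, so 19 days are lost. Exit on Day 36, 43 or 50 loses 12, 5 or 0 days.

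**The case against.** The strongest objection concerns patient care. The Synopsis and 5.1 tie rescue to deterioration and otherwise freeze SoC, and 7.9.1 does not list a cholinesterase-inhibitor increase. On that reading, the lack-of-efficacy item is what releases a stable but symptomatic non-responder to other treatment. Section 7.9.2 is broader, allowing "increase in the dose and frequency of SoC or any other treatment chosen by the Investigator", but the sections are not aligned. This objection stands: deleting the item without aligning them could leave such a patient with no clear route to changed treatment.

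Second, on the broad reading of 7.9.2 the item may add few exits. Non-responders who need treatment leave through rescue anyway, and no dosing remains after Visit 7. This also stands; the documents support no particular trigger.

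Third, the modelled by-visit comparison is largely protected, and Protocol 10.4.2.1 also plans a last-observation-carried-forward figure that keeps leavers (the SAP does not repeat it). That limits the point to the observed displays, maximum reduction and some precision.

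A reader might infer that the rule biases the trial's efficacy comparison as a whole, or that lack of efficacy is the only outcome-driven exit. The documents support neither: the MMRM uses all recorded scores including the mapped exit visit, and deterioration during treatment and rescue also end participation. Nor is 0.70 a bias in the treatment difference in general. It is a placebo-arm figure, and it shrinks when active patients also leave.

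**Conclusion.** The point holds as a low-cost improvement to consider, with medium confidence. As written, the rule discards later data because of the outcome, whereas Table 2 tries to keep data after several other events.

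The size cannot be derived from the plan, which gives neither an exit rate nor a trigger. Under the stated assumptions the later observed placebo mean is 0.13 to 0.70 points too favourable. With a 2-point effect and equal SDs, the observed difference narrows by about 0.15 to 0.35 (2-point cut) or 0.08 to 0.21 (1-point cut). Maximum reduction is distorted in the drug's favour, through a placebo understatement of 0.05 to 0.26, so the overall effect is not simply conservative. The MMRM result depends on exit following recorded scores.

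The harm is limited. Efficacy is secondary and exploratory, p-values are descriptive, and SAP 9 tabulates the primary reason for study discontinuation. An imbalance would therefore be visible, although the table cannot recover the lost data.

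**What to change.** Amend the protocol as follows:

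- Remove lack of efficacy from the mandatory study-exit list in 5.3.4 and make it at most a reason to stop IMP.
- Add a Table 2 row under which such patients continue scheduled safety and efficacy assessments to Visit 16 wherever possible and appropriate, reusing the table's existing wording.
- State that physician decision is not used as the exit reason for lack of efficacy alone.
- Align the Synopsis and 5.1 with 7.9.2, so that a non-improving patient who needs any change of MG treatment, including a cholinesterase-inhibitor increase, may receive it as rescue.
- Leave exits for rescue (7.9.2) and prohibited medication (7.9.1) unchanged.

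The cost is a short amendment. Some non-improving patients would attend further visits on unchanged SoC, and those on cholinesterase inhibitors would face up to 5 more 12-hour holds after Visit 9 (Visits 10, 11, 12, 14 and 16). Rescue and withdrawal of consent remain open to them.
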